**Table 16: Censoring Rules for antineoplastic therapy**

Situation	End Date on or prior to cut-off date	Censored
Recorded antineoplastic therapy during the study	Date of the first assessment that qualified as antineoplastic therapy	No
Death during the study before antineoplastic therapy	Date of last visit at which antineoplastic therapy question was collected or randomization date whatever comes later	Yes
Patient has no recorded antineoplastic therapy at data cut-off	Date of last visit at which antineoplastic therapy question was collected or randomization date whatever comes later	Yes
Patient lost to follow-up before data cut-off	Date of last visit at which antineoplastic therapy question was collected or at the data cut-off, whichever occurs first	Yes

This endpoint is selected from the ADTTE dataset using variable PARAMCD equal to 'ISAT'.

A log rank test stratified by same stratification factors used in the MFS analysis will be used to compare the darolutamide treated and placebo groups.

The hazard ratio as well as its 95% CI will be generated with a Cox regression model as for MFS.

Kaplan-Meier survival curves (product-limit estimates) will be presented by treatment arm. The Kaplan-Meier estimate of the median time to initiation of subsequent antineoplastic therapy and first and third quartiles will be presented with 95% CIs.

A summary of first subsequent antineoplastic therapy will be provided.

#### 6.2.3.4 Time to PSA progression

Time to PSA progression is defined as the time (days) from the date of randomization to the date of first PSA progression.

PSA progression is defined according to the Consensus Guidelines of the Prostate Cancer Trials Working Group2 (PCWG2) as:

For patients with no decline from baseline at week 16, the PSA progression is defined as the date that a  $\geq 25\%$  PSA increase in PSA along with an absolute increase of  $\geq 2$  ng/ml above the baseline is documented, which is confirmed by a second consecutive value obtained 3 or more weeks later,

Or

For patients with declines from baseline at week 16, the PSA progression is defined as the date that a  $\geq 25\%$  PSA increase and an absolute increase of  $\geq 2$  ng/ml above the nadir is documented, which is confirmed by a second consecutive value obtained 3 or more weeks later.

The above PSA definition deviate from PCWG2, as confirmation by a second value is requested here for a patient with no decline from baseline.

Early increases in PSA values before the 16 weeks are not considered as PSA progression.

PSA documented post end of study-treatment visit will not be considered. Central laboratory assessment will be considered.

Baseline PSA value is the last non-missing observation on or before the first day of study drug intake.

Table 17 will be used for calculating the time to PSA progression. Time to PSA progression = End Date - Date of randomization + 1.

**Table 17: Censoring Rules for PSA progression**

Situation	End Date on or prior to cut-off date	Censored
No baseline or post-baseline PSA assessment	Date of randomization	Yes
No PSA progression	Last PSA assessment date	Yes
Patient had an PSA progression	The date of first observation of PSA progression	No
PSA progression after two or more consecutive missed PSA assessments	Date of last PSA assessment before missed assessments	Yes

This endpoint is selected from the ADTTE dataset using variable PARAMCD equal to ‘TTCPP’.

Time to PSA progression will be analyzed with the same methods as the primary variable MFS. A log rank test stratified by the same factors as used for randomization will be used to compare the darolutamide treated and placebo groups. Kaplan-Meier curves, median survival times, and their 95% CI will be presented. Hazard ratios will be calculated with the Cox model.

### 6.2.3.5 Percent of patients with PSA response

The percentage change of PSA from baseline at any time point will be calculated and the proportion of patients achieving a decline of  $\geq 50\%$  from baseline will be determined.

PSA values will be collected until the end-of-study treatment visit.

PSA response rate will be compared between treatment groups using Cochran-Mantel-Haenszel test adjusting for same stratification factors as for primary endpoint. Estimates and the 95% CI will be computed for each treatment group.

Sample code for Cochran-Mantel-Haenszel test:

```
proc freq data=data;
tables psa_double*ot_therapy*PSA_Response*trtpn /CMH;
run;
```

Where:

*PSA\_Response* contains corresponding PSA Response values, *trtpn* contains assigned treatment group, *psa\_double* contains PSA doubling time category at randomization, *ot\_therapy* contains category for osteoclast-targeted therapy use at randomization.

In addition, descriptive statistics will be provided for PSA at baseline, 16 weeks, change from 16 weeks to baseline, maximum percent decline from baseline at any time on study.

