6.1.2.6 End-of-study treatment visit, and in transition to the roll-over study

Patients will have an end-of-study treatment visit 28 days (+7 days) after the last dose of study treatment or before transition to the roll-over study. Another systemic antineoplastic therapy may be initiated no sooner than 7 days after the last dose of study treatment.

Note: the end-of-study treatment visit procedures for placebo patients crossing over to open-label darolutamide treatment are described in [Table 4](#) instead.

The following procedures will be performed during the end-of-study treatment visit:

- BPI-SF, FACT-P, EORTC-QLQ-PR25 and EQ-5D-3L questionnaires
- Physical examination including weight
- Only for the double-blind treatment period: A 12-lead ECG in a supine position after at least 10 minutes rest. An ECG with a QTcF > 500 ms should be confirmed by a second ECG taken 1-2 hours later
- BP and HR (unless recorded by ECG) in a supine position after at least 10 minutes rest
- Laboratory safety assessments (haematology, chemistry and urinalysis) and PSA
- A blood (plasma) sample for tumour-related biomarker analysis unless precluded by local guidelines, e.g. IEC/IRB or regulatory authorities (see [Section 6.5](#))
- ECOG performance status
- Date of first SSE
- Date of first prostate cancer-related invasive procedure
- Status of survival
- Current medical condition, AEs and concomitant treatments
- Collection of pain diary and dispensing a new pain diary. No pain diary will be dispensed when a patient is transitioning to the roll-over study.

- Return of all remaining study drugs and study drug containers and drug accountability performed

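### PSA response counts values drawn after the next antineoplastic therapy may have started, so another drug's effect can be scored to the randomised arm, in either arm

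*SAP*

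**What the plan says.** Protocol 6.1.2.6 sets both ends of the window. On the visit: "Patients will have an end-of-study treatment visit 28 days (+7 days) after the last dose of study treatment". On the next therapy: "Another systemic antineoplastic therapy may be initiated no sooner than 7 days after the last dose of study treatment". The 7-day rule also appears in protocol 4.7.1 and 5.7.2. PSA is among the visit procedures: "Laboratory safety assessments (haematology, chemistry and urinalysis) and PSA".

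For PSA response, SAP 6.2.3.5 reads: "The percentage change of PSA from baseline at any time point will be calculated". It then takes the proportion with a fall of at least 50%. On the data window it says: "PSA values will be collected until the end-of-study treatment visit". The same section summarises the largest percentage decline seen during the study.

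For time to PSA progression, SAP 6.2.3.4 excludes only later values: "PSA documented post end of study-treatment visit will not be considered". A rise counts only if it meets this condition: "which is confirmed by a second consecutive value obtained 3 or more weeks later". A patient without progression is censored under Table 17 at the "Last PSA assessment date". None of the four rows of Table 17 concerns new anticancer therapy, and 6.2.3.5 has no such exclusion either.

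SAP 6.2.3 gives the p-values of these endpoints informative status only.

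**The concern.** A PSA response should describe what happened under the assigned treatment. Here a value can be taken while the patient is on a different drug, and a single qualifying value is enough. The amendment history (Amendment 1, Modification 12) explains the overlap: the visit for patients starting subsequent therapy was moved from 7 to 28 days after the last dose so that adverse events could be collected. The PSA derivation has no matching cut.

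The effect of darolutamide on PSA response and progression is a listed additional objective, and the SAP plans tests and confidence intervals for it. At stake are the response rate in each arm, the summary of maximum decline and, through the confirmation rule, some progression events. MFS and the secondary endpoints do not use these values.

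**Working it through.** The plan gives no figure for this point, and the MFS event target and power do not depend on it.

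**1. Length of the overlap.** Inputs: day 7 and day 28 to 35 after the last dose (protocol 6.1.2.6). 28 − 7 = 21 days; 35 − 7 = 28 days. A patient who starts at the earliest permitted time has 21 to 28 days of the next drug before the PSA is drawn; one who starts later has less.

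**2. Size of fall needed.** Response is measured from baseline, not from PSA at withdrawal. If PSA has grown by a factor g = 2^(t/PSADT), the fall needed from the current value is 1 − 0.5/g. Entry requires a PSADT of 10 months or less; 6 months is the stratum boundary. Week 16 is 112/30.44 = 3.68 months.

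| Time | PSADT | g | Fall needed |
|---|---|---|---|
| Week 16 | 10 months | 1.29 | 61% |
| Week 16 | 6 months | 1.53 | 67% |
| 12 months | 10 months | 2.30 | 78% |
| 12 months | 6 months | 4.00 | 87.5% |

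A placebo patient whose PSA has kept rising needs a fall of this size within 28 days at most. That can happen, but it limits the number of false responders. On darolutamide, most responders have already been counted. A non-responder's PSA may be nearer baseline, so a smaller fall is enough.

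**3. Rate of reaching an MFS event, a main route into the window.** With a placebo median of 25 months and a hazard ratio of 0.65 (SAP 3.1), the proportion with metastasis or death by 12 months is 1 − 2^(−12/25) = 28.3% on placebo and 1 − 2^(−12 × 0.65/25) = 19.4% on darolutamide. The rate is higher on placebo. With 500 and 1000 patients the counts are about 142 and 194, so the number is higher on darolutamide.

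**4. Illustrative size.** This simulation (20,000 patients per arm and scenario) rests on assumptions that are not in the documents:
- 30%, 60% or 90% of patients who stop begin a new drug between day 7 and day 28.
- The median PSA ratio after 28 days of that drug is 0.3 or 0.5.
- PSADT is 2 to 10 months, 85% respond on darolutamide, and stopping without metastasis runs at 1% per month.

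Each entry compares the present rule with the same visit value had no new drug been given, in percentage points of the arm.

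| Start new drug | PSA ratio | Added responders, placebo | Added responders, darolutamide | Lost confirmations, placebo | Lost confirmations, darolutamide |
|---|---|---|---|---|---|
| 30% | 0.3 | 0.50 | 0.43 | 1.81 | 0.41 |
| 30% | 0.5 | 0.13 | 0.19 | 1.01 | 0.22 |
| 60% | 0.3 | 0.94 | 0.88 | 3.50 | 0.66 |
| 60% | 0.5 | 0.20 | 0.49 | 2.16 | 0.42 |
| 90% | 0.3 | 1.59 | 1.27 | 5.13 | 1.12 |
| 90% | 0.5 | 0.47 | 0.65 | 3.16 | 0.68 |

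The change in the between-arm difference in response (darolutamide minus placebo) runs from 1.27 − 1.59 = −0.32 to 0.49 − 0.20 = +0.29 points, so its direction is not fixed.

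**5. Progression.** Suppose the first qualifying rise is at the visit whose scan shows metastasis. Protocol Table 4 schedules no PSA after confirmed metastasis, so the end-of-study treatment value is the only scheduled confirmation. If the next drug has lowered it, the rise is unconfirmed and the patient is censored. Dropping the value does not help, because the rise then has no confirming value at all. Dropping it also removes events now confirmed at that visit despite the new drug.

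**The case against.** The case for leaving the plan alone has four parts.

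- **The endpoints are tertiary.** This stands, and it limits the weight of the point.
- **Following PSA to a fixed visit whatever therapy is started is a legitimate estimand, and censoring at a switch can itself be informative.** This stands for progression and is the reason not to replace that rule. It is weaker for response, because the SAP does not state such an intention and a single unconfirmed value decides the outcome.
- **Patients who start prohibited therapy before metastasis are followed only for survival** (protocol section 3 and the note under Table 4). This limits the overlap for them, but protocol 4.7.1 still invites them to the 28-day visit. It does not cover therapy begun after confirmed metastasis.
- **The MFS and PFS censoring rows for new treatment are not a like-for-like precedent.** This stands: they concern prohibited treatment started before metastasis (or, for PFS, local progression), whereas much of the overlap here comes after metastasis.

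A reader might infer a much larger effect on placebo. Suppose 40–60% stop, 20–60% of these start a new drug before the visit, and 20–60% of those show a halved PSA. The product runs from 0.4 × 0.2 × 0.2 = 1.6% to 0.6 × 0.6 × 0.6 = 21.6%. None of the three shares is in the documents, and the third is credible only if the fall is taken from PSA at withdrawal. The SAP takes it from baseline.

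**Conclusion.** The gap is real for PSA response. A value taken after up to 21 to 28 days of another drug can be scored as a response to the assigned treatment, in either arm. The documents permit this but do not show how often it occurs. On the assumptions above it adds about 0 to 2 percentage points per arm.

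A reader might also infer that the effect falls mainly on placebo and pulls both PSA comparisons towards no difference. The documents do not support that for response: the added responders are similar in the two arms. For progression the inference is plausible, since the simulated loss of confirmations is 1.0 to 5.1 points on placebo against 0.2 to 1.1 on darolutamide. Those figures rest on the same assumptions, the direction would count against darolutamide, and a cut at the new therapy would not recover the events.

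This is a cheap improvement to tertiary analyses. It does not bear on the primary or secondary conclusions.

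**What to change.** 1. **PSA response and maximum percentage decline (SAP 6.2.3.5).** Disregard PSA values on or after the start of any subsequent systemic antineoplastic therapy, not only therapy classed as prohibited. Combine the drug lists in SAP 9.7 and 9.8, because 9.8 leaves out the cytotoxic classes. Exempt continuing GnRH therapy, which falls within the endocrine class in 9.8. Keep the present rule as a sensitivity analysis.
2. **Time to PSA progression (SAP 6.2.3.4, Table 17).** Keep the present rule. Add a sensitivity analysis that censors at the last PSA before the new therapy, and state that it may remove events confirmed at the end-of-study treatment visit.
3. **Protocol consistency.** Reconcile section 3 and the note under Table 4 with 4.7.1 on whether the visit PSA is taken in patients who start prohibited therapy before metastasis.

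No change to the timing of treatment or visits is proposed. The cost is one date filter and one extra analysis, because protocol 5.7.1 and 6.1.3 already provide for recording these therapies. The downside is that a few PSA values after a switch are not used in the main response analysis.

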#### 6.2.3.6 Percent of patients with ECOG performance status deterioration

ECOG performance status (PS) is assessed at screening and every 16 weeks until the end of follow-up period.

ECOG PS will be tabulated and summarized by visit for observed values and changes from baseline using descriptive statistics, as appropriate. If more than one baseline assessment was collected, the most recent one will be used. If several assessments were performed on the same day (without timing information) the most severe score will be used.

ECOG performance status deterioration is defined as an increase to grade 3 or higher, with an increase of at least 2 from baseline.

Deterioration will be compared between treatment groups using Cochran-Mantel-Haenszel test adjusting for same stratification factors as for primary endpoint. Estimates and the 95% CI will be computed for each treatment group.

#### 6.2.3.7 Time to ECOG performance status deterioration

Time from randomization to ECOG performance status deterioration is defined as time from randomization to ECOG PS deterioration.

Table 18 will be used for calculating the time to ECOG performance status deterioration. Time to ECOG performance status deterioration event = End Date-Date of randomization +1.

**Table 18: Censoring Rules for ECOG performance status deterioration**

Situation	End Date on or prior to cut-off date	Censored
Recorded ECOG PS deterioration during the study	Date of the first ECOG PS deterioration	No
No ECOG PS deterioration during study	Date of last ECOG PS assessment	Yes
Patient has no post baseline ECOG PS assessment at data cut-off	Date of randomization	Yes

This endpoint is selected from the ADTTE dataset using variable PARAMCD equal to 'ECOGDET'.

A log rank test stratified by same stratification factors used in the MFS analysis will be used to compare the darolutamide treated and placebo groups.

The hazard ratio as well as its 95% CI will be generated with a Cox regression model as for MFS.

Kaplan-Meier survival curves (product-limit estimates) will be presented by treatment arm. The Kaplan-Meier estimate of the median time to ECOG PS deterioration and first and third quartiles will be presented with 95% CIs.

**6.2.3.8 Time to first opioid use for cancer pain**

Time to first opioid use for cancer pain is defined as time from randomization to first opioid use for cancer pain.

List of opioids for cancer pain is available in Appendix 9.10.

Table 19 will be used for calculating the time to Time to first opioid use for cancer pain. Time to first opioid use for cancer pain = End Date-Date of randomization +1.

**Table 19: Censoring Rules for Time to first opioid for cancer pain**

Situation	End Date on or prior to cut-off date	Censored
Recorded opioid use for cancer pain during the study	Date of first opioid use	No
No opioid use for cancer pain during study	Date of last visit	Yes
Patient has no post baseline assessment at data cut-off	Date of randomization	Yes

This endpoint is selected from the ADTTE dataset using variable PARAMCD equal to ‘OCP’.

A log rank test stratified by same stratification factors used in the MFS analysis will be used to compare the darolutamide and placebo groups.

The hazard ratio as well as its 95% CI will be generated with a Cox regression model as for MFS.

Kaplan-Meier survival curves (product-limit estimates) will be presented by treatment arm. Kaplan-Meier estimates of the median time and first and third quartiles times will be presented with 95% CIs.

**6.2.3.9 Health related Quality of Life and utility values.**

1) The **EQ-5D-3L** is a generic quality of life preference based instrument which has been validated in cancer population to measure both utility and health status.

The EQ-5D-3L contains a descriptive system which measures 5 health dimensions: mobility, self-care, usual activity, pain/discomfort, and anxiety/depression. Each dimension contains 3 levels of response to reflect the degree of problems patients have experienced: no problem (level 1), some problems (level 2), and extreme problems (level 3). These five health

dimensions are summarized into a single score, the EQ-5D-3L index score. The EQ-5D-3L index score ranges -0.59 to 1 with higher scores representing better health states.

The EQ-5D-3L also contains a visual analog scale (EQ-VAS), which records the respondents' self-rated health status on a vertical graduated visual analogue scale ranging from 0 (worst imaginable health state) to 100 (best imaginable health state).

For details on scoring, please refer to the EQ-5D-3L user guide Appendix 9.5.

Since EQ-5D-3L is a descriptive system based on five independent dimensions, a missing answer or ambiguous answer (i.e. marking of more than one level on scale) will lead to complete rejection of the questionnaire, but the VAS score will be retained if available.

2) The **FACT-P** questionnaire assesses prostate cancer-related quality of life and has been validated in the prostate cancer population.

This questionnaire contains 5 domains: Physical Well-Being (PWB), Social/Family Well-Being (SWB), Emotional Well-Being (EWB), Functional Well-Being (FWB), and Additional Concerns (also called Prostate cancer subscale [PCS]).

According to the FACT-P scoring guide, all subscale items are summed to a total which is the subscale (=domain) score. The FACT-P total score is the sum of the scores of 39 items of the questionnaire and ranges from 1 to 156; the higher the score, the better the quality of life of prostate cancer patients.

Each item can be answered on a 5-point (0–4) scale.

The sum of the scores on the first four domains (PWB, SWB, EWB, and FWB) constitutes the FACT-G (General). The sum of the scores on all five domains constitutes the FACT-P. The trial outcome index (TOI) is derived by the sum of PWB, FWB, and PCS scores.

For details on scoring, please refer to the FACT-P user guide Appendix 9.3.

In case of missing responses for one or more items, subscale scores can be prorated. This is done by multiplying the sum of the subscale by the number of items in the scale, then dividing the number of items actually answered. Prorating of scores is acceptable as long as more than 50% of the items are answered (assuming that the score of missing items are similar to those of non-missing items). If less than or equal to 50% of the items are answered for any domain, then the score of that specific domain is set to missing. The FACT-P total score is then calculated as the sum of the un-weighted subscale scores. Moreover, the FACT-P total score is set to missing if the related overall item response rate is less than or equal to 80%.

The total score is then calculated as the sum of the un-weighted subscale scores. A total score is calculated if all of the component subscales have a valid score.

Rate of the question GS7 'I am satisfied with my sex life' in the SWB domain will be used independent of the answer documented in the question Q1 "Regardless of your current level of sexual activity, please answer the following question. If you prefer not to answer it, please check this box and go to the next section".

3) The **BPI-SF** questionnaire assesses clinical pain related to cancer, it is a validated tool. Two scores will be derived: the pain severity and the pain interference.

Questionnaire is completed daily over a 7-day period. Averages during the period of reporting are calculated. If fewer than 4 reports out of the 7 days are available at the planned time point for assessment, this would constitute missing data.

The BPI assesses pain at its “worst” “least” “average” and “right now” (current pain). To derive the “pain severity” score a mean score of the 4 questions (questions 3 to 6 from the BPI-SF) related to pain will be created. In case of one or more missing information the “pain severity” score will be assessed to missing.

The BPI measures how much pain has interfered with seven daily activities, including general activity, walking ability, normal work, mood, enjoyment of life, relations with others, and sleep (question 9 from the BPI-SF). BPI “pain interference” is scored as the mean of the seven interference items. This mean can be used if more than 50% or four of seven, of the total items have been completed on a given administration.

Rate of pain entered in questions 3 to 9 will be used independent of the answer documented in the question 1 (have you had pain other than these everyday kinds of pain today) of the BPI-SF.

For details on scoring, please refer to the BPI-SF user guide Appendix 9.2.

4) The **EORTC-QLQ-PR25** questionnaire assesses prostate cancer-related quality of life and has been validated in the prostate cancer population.

The prostate cancer module is a 25-item questionnaire designed for use among patients with localized and metastatic prostate cancer. It includes subscales assessing urinary symptoms (8 items), bowel symptoms (4 items), hormonal treatment-related symptoms (6 items), incontinence aid (1 item), sexual activity (2 items) and sexual functioning (4 items). The sexual activity and sexual functioning scales constitute the functional scales. The urinary symptoms, bowel symptoms, hormonal treatment-related symptoms, and incontinence aid constitute the symptom scales.

If less than or equal to 50% of the items are answered for any subscales, then the score of that specific subscale is set to missing.

For details on scoring, please refer to the EORTC-QLQ-PR25 user guide Appendix 9.4.

